5.4.1.	Definition	
5.4.2.	Analysis Methods	. 18
	SAFETY	
6.1.	Adverse Events	. 19

Statistical Analysis Plan 56021927PCR4007

REF	FERENCES	2
7.	PHARMACOKINETICS/PHARMACODYNAMICS	2
	Electrocardiogram	
	Vital Signs and Physical Examination Findings	
6.2	Clinical Laboratory Tests	20

AMENDMENT HISTORY

SAP Version	Issue Date
Amendment 1	12Jul2023
Original SAP	30Apr2020

Amendments below are listed beginning with the most recent amendment.

Amendment 1 (12Jul2023)

Applicable Section(s)	Description of Change(s)	Rationale
Section 1.2. Trial Design; Section 1.4. Sample Size Justification; Section 1.5.2. Blinding; Section 3. INTERIM ANALYSIS AND DATA MONITORING COMMITTEE REVIEW	 Changed the number of participants to be enrolled from 111 to 75. Removed the interim analysis. Revised the role of Independent Data Monitoring Committee (IDMC). Revised the unblinding circumstance. 	The change was made based on CDE consultation outcome and to align with protocol amendment 3. Since interim analysis is not applicable anymore and study will be unblinded at the final analysis, the role and responsibility of IDMC was also revised.
Section 2.2. Pooling Algorithm	Added the pooling algorithm for stratification factors.	Stratified analysis may lead to reduced statistical power if the sample size within each stratum is small.
Section 4.2. Disposition Information; Section 4.5. Protocol Deviations; Section 5.2.3 Analysis Method; Section 6.1. Adverse Events	Added analyses for COVID-19 related data in applicable sections.	To explore the potential impact of the COVID-19 pandemic on the study outcomes, additional analyses were added.
Section 5.2.2. Estimand	 Intercurrent events of clinical cutoff and treatment discontinuation were deleted. The strategy name for treatment switching and subsequent anti-cancer was revised. 	Clinical cutoff is a pre-determined timepoint; treatment discontinuation in this study will lead to an administrative stop of subsequent PSA testing. Neither are considered intercurrent events. The strategy name was adjusted according to the definition of each strategy in ICH E9(R1).

Section 5.2.3. Analysis Methods	 Sensitivity analysis regarding additional censoring rules for TTPP event dates was deleted. Revised the time point to estimate the PSA progression-free rate from "6-month, 1-year and 2-year" to "at selected timepoints". 	The additional censoring rule for TTPP event dates explores an alternative clinical question of interest (Estimand), which differs from the primary objective in its focus and assumption. Considering the censoring rule of placebo arm, the estimating timepoints were revised.
Section 5.3.2. Analysis Methods	 Added Fisher's exact test. Added PSA response by Week 12. 	Fisher's Exact Test may provide a more accurate assessment of associations in the contingency table when some cells have low counts. PSA response by Week 12 can provide valuable insights and comprehensive understanding into the treatment effect.
Section 6.1. Adverse Events	Narrative criteria were revised.	The narrative criteria were revised to keep consistent with SPARTAN study.
Throughout the SAP	Minor grammatical, formatting, or spelling changes were made.	Minor errors were noted.

ABBREVIATIONS

ADT androgen deprivation therapy

AE adverse event
CI confidence interval
CRF case report form

CRPC castration-resistant prostate cancer

CSR Clinical Study Report

CTCAE Common Terminology Criteria for Adverse Events

ECG Electrocardiogram

ECOG Eastern Cooperative Oncology Group

eCRF electronic case report form

EoT end of treatment

GnRH gonadotropin releasing hormone

HR hazard ratio IA Interim Analysis

IDMC Independent Data Monitoring Committee

ITT Intent-to-Treat

IWRS interactive web response system

K-M Kaplan-Meier

NM-CRPC non-metastatic castration-resistant prostate cancer MedDRA Medical Dictionary for Regulatory Activities

MFS metastasis-free survival MRI magnetic resonance imaging

OS overall survival

PCWG2 Prostate Cancer Working Group 2

PK pharmacokinetic(s)
PSA prostate specific antigen

PSADT prostate specific antigen (PSA) doubling time

SAE serious adverse event
SAP Statistical Analysis Plan
SD standard deviation
SOC system organ class
SRE skeletal related events

TTPP time to prostate specific antigen (PSA) progression

WHO World Health Organization

1. INTRODUCTION

This statistical analysis plan (SAP) describes the definitions of analysis sets, derived variables, and statistical methods for all planned statistical analyses in protocol 56021927PCR4007.

1.1. Trial Objectives

Primary Objectives:

To compare the improvement in time to prostate specific antigen (PSA) progression (TTPP, as defined by Prostate Cancer Working Group 2 [PCWG2]) of apalutamide versus placebo in Chinese subjects with high risk NM-CRPC.^[1]

Secondary Objectives:

- To evaluate the safety and tolerability of apalutamide
- To compare the prostate-specific antigen (PSA) response rate in Chinese subjects with high risk NM-CRPC treated with apalutamide versus placebo
- To evaluate the pharmacokinetics (PK) of apalutamide

Exploratory Objectives:

- To evaluate the metastasis-free survival (MFS) of Chinese subjects with high risk NM-CRPC treated with apalutamide
- To evaluate the overall survival (OS) of Chinese subjects with high risk NM-CRPC treated with apalutamide
- To evaluate the time to symptomatic progression in Chinese subjects with high risk NM-CRPC treated with apalutamide

1.2. Trial Design

This is a randomized, double-blind, placebo-controlled, multicenter, Phase 4 study evaluating the efficacy and safety of ADT plus apalutamide versus ADT plus placebo in Chinese subjects with high-risk NM-CRPC.

[figure not shown]
The study will consist of 4 phases: an optional Prescreening Phase, a Screening Phase (≤35 days prior to randomization); a Treatment Phase (starting on day 1 of cycle 1 until disease progression/ unacceptable toxicity, withdrawal of consent, death or termination of the study) and a post-treatment Follow-up Phase (starting after end-of-treatment visit until death, withdrawal of consent for study participation, or termination of the study).

Approximately 75 Chinese subjects who meet all the inclusion criteria and none of the exclusion criteria will be randomized in a 2:1 ratio to receive apalutamide or matching placebo. Subjects will be stratified by PSADT (>6 months vs. ≤6 months). Apalutamide or matched placebo will be administered orally on a continuous daily dosing schedule at a starting dose of 240 mg per day in the Treatment Phase. ADT with gonadotrophin-releasing hormone agonists (GnRHa) will be continued for all patients who have not been surgically castrated. Subjects randomized to the

placebo arm who do not have evidence of distant metastasis (according to imaging result at Cycle 5 Day 1, as well as at any other relevant unscheduled visit) will be crossed over and start receiving active therapy of apalutamide after completion of 5 cycles of placebo + ADT treatment (handling by the IWRS). Placebo subjects who have documented PSA progression prior to completion of 5 cycles of study treatment, will cross over to apalutamide at the time of PSA progression. Any subjects who develop distant metastasis at any time on study will discontinue study treatment and may receive subsequent therapy as per standard of care.

Subjects will be followed for safety and efficacy as per the schedule of activities and will remain on study treatment until development of distant metastases as assessed by investigators or the development of unacceptable toxicity or the study end defined as MFS events observed in approximately 60% of the study population or 3 years after the final analysis for the primary endpoint TTPP, whichever comes first. An End of Treatment (EoT) Visit will occur approximately 30 days of the last dose of study treatment. The Post-treatment Follow-up Phase will begin after the EoT visit. Subjects will be contacted every 4 months to obtain survival status, recording of development of symptomatic progression, initiation of any new systemic anti-cancer therapies until death, withdrawal of consent for study participation, or termination of the study. The final analysis for the primary endpoint TTPP will occur at 5 months after the last subject received the first dose.

Figure 1

Note: ADT: androgen deprivation therapy, being either surgical castration or gonadotrophin-releasing hormone agonists (GnRHa), will be continued as background therapy for all subjects. ADT with GnRHa will be continued for all patients who have not been surgically castrated.

1.3. Statistical Hypotheses for Trial Objectives

The primary hypothesis of this study is that subjects receiving treatment with apalutamide will have a longer TTPP compared with subjects receiving placebo. The null hypothesis of this study is no difference between these two treatment groups in TTPP.

1.4. Sample Size Justification

Subjects randomized to the placebo arm who do not have evidence of distant metastasis (according to imaging result at Cycle 5 Day 1, as well as any other relevant unscheduled visit) will start receiving active therapy of apalutamide at the time they have documented PSA progression (per PCWG2) or after completion of 5 cycles of placebo+ADT treatment (handling by the IWRS). Any subjects who develop distant metastasis at any time on study will discontinue study treatment, and may receive subsequent therapy as per standard of care.

It is assumed that failure distribution of the primary endpoint TTPP follows an exponential distribution with a constant hazard rate. The pivotal SPARTAN study suggested that East Asian subjects treated with ADT would only have a median TTPP of 3.7 months. It is estimated that a sample size of 75 subjects with follow-up continued up to approximately 5 months after last subject dosed will provide approximately 28 TTPP events to yield a power exceeding 95% for detecting a hazard ratio (HR) of 0.11 (median TTPP of 3.7 months for the placebo arm versus 33.6 months for the apalutamide arm, here 0.11 is the upper limit of 95% CI in the TTPP results of East Asian) at a 2-tailed significance level of 0.05. With a 32-month accrual period and an additional 5-months of follow-up, the study duration for the TTPP final analysis will be approximately 37 months.

1.5. Randomization and Blinding

1.5.1. Randomization

Subjects who meet all the inclusion criteria and none of the exclusion criteria will be randomized in a 2:1 ratio to receive apalutamide or placebo. Subjects will be stratified by the following factor for randomization:

• PSADT: >6 months vs. ≤6 months

Randomization will take place across all study sites using a centralized Interactive Web Response System (IWRS).

To ensure an accurate and consistent determination of PSADT across all sites, the IWRS will provide PSADT calculations (using a linear regression model of the normal logarithm of PSA and time) based on at least 3 PSA values obtained during continuous ADT. All available consecutive PSA values obtained within 24 months prior to randomization beginning with the earliest value chosen for the PSADT calculation must be entered in the IWRS. The first and last PSA values used in the calculation must be separated by at least 8 weeks.

Those same PSA values will be used during Screening to determine whether the patient is eligible for the study (inclusion criterion #3). To pre-screen subjects for possible enrollment into the study, PSADT can be calculated using the Memorial Sloan-Kettering Cancer Center (MSKCC) PSADT prediction tool, available at the following website:

http://nomograms.mskcc.org/Prostate/PsaDoublingTime.aspx

1.5.2. Blinding

All subjects and study team members associated with the study conduct are to remain blinded to treatment group assignment until final analysis. Unblinding before final analysis may only occur in case of safety or medical emergency.

PSA will be collected and analyzed by a central laboratory but investigators, participants, and the Sponsor will be blinded to the results until the full unblinding of the study. The cross-over of control group subjects will be handled by IWRS to maintain the blinding of original individual treatment assignment. Control group subjects without distant metastasis will switch to treatment with apalutamide plus ADT at the time PSA progression (per PCWG2) is documented or subjects have completed 5 cycles treatment of placebo + ADT. The PSA data collected at baseline and post-baseline obtained within the first 5 cycles, for individual subject will be analyzed by the central lab to flag out documented PSA progression per PCWG2. The data will be integrated into the IWRS to trigger the cross-over.

2. GENERAL ANALYSIS DEFINITIONS

Study Day is calculated in reference to the date of randomization for efficacy analyses and date of first dose for safety analyses (efficacy analysis Study Day 1 = date of randomization; safety analysis Study Day 1 = date of first dose). Positive study days will count forward from Study Day 1. Study Day -1 will be the day before Study Day 1, and all subsequent negative study days will be measured backward from Study Day -1. There will be no Study Day 0.

The first dose starts on Day 1 of Cycle 1.

Unless otherwise specified, baseline value is defined as the closest measurement prior to the first dose of study drug. Change from baseline will be defined as (post-baseline value – baseline value).

Treatment Duration is calculated as the duration of time from the date of the first dose of study drug to the date of last dose of the study drug, ie, date of last dose – date of first dose + 1.

Time to Event is calculated as the number of days from randomization to the date of the event of interest, ie, date of event of interest – date of randomization + 1. Time to event endpoints will be based on the actual date of the event, not visit number or visit label.

Continuous/numerical variables will be summarized using mean, standard deviation (SD), median, minimum, and maximum. Categorical variables will be summarized using count and percentage. In general, means and other measures of central tendency will be displayed with one more decimal digit than collected, and standard deviations and other measures of variability will be displayed with two decimal digits more than collected. For frequency counts of categorical variables, categories for which the counts are zero will be displayed for the sake of completeness. For example, if no subject discontinued due to "withdrawal of consent", this reason would still be included in the table but with a count of 0.

2.1. Visit Windows

The Treatment Phase will begin at Cycle 1 Day 1 of treatment and will continue until study drug is discontinued. Nominal visits will be used to display the safety data.

2.2. Pooling Algorithm for Analysis Centers and Stratification Factors

There is no plan in pooling the centers (study sites) for efficacy or safety analyses, unless analysis by site is warranted. The stratification factor to be used in the analysis is PSADT. For efficacy analyses, if any stratum has few events (for time-to-event endpoint) or participants (for categorical endpoint) for any treatment arm, then the subjects will be pooled together by dropping the stratification factor.

2.3. Analysis Sets

2.3.1. Efficacy Analysis Set

The Intent-to-Treat (ITT) analysis set includes all randomized subjects and will be classified according to their assigned treatment group, regardless of the actual treatment received. Subject disposition, demographics and baseline characteristics, as well as efficacy analyses will be performed on data from the ITT analysis set.

2.3.2. Safety Analysis Set

The safety analysis set includes all randomized subjects who received at least 1 dose of study drug, with treatment assignments designated according to actual study treatment received. The safety analysis set will be used in the analyses of safety and treatment compliance.

2.3.3. Pharmacokinetics Analysis Set

The PK analysis set is defined as all subjects who have received at least one dose of apalutamide and have at least one quantifiable plasma concentration.

2.4. Definition of Subgroups

In order to assess the consistency of treatment benefit across different subject subpopulations, the planned analyses may also be carried out using the following subgroups in TTPP (see Section 5):

- ECOG performance status (0 vs. 1) at baseline
- Age category ($< 65 \text{ vs.} \ge 65 \text{ years and} < 75 \text{ vs.} \ge 75 \text{ years}$)
- Number of prior hormonal therapies $(1 \text{ vs.} \ge 2)$
- PSADT (> 6 months vs. \leq 6 months)

2.5. Study Day and Relative Day

Study Day 1 or Day 1 refers to the start of the first study drug administration for safety analysis or randomization date for efficacy analysis. All efficacy and safety assessments at all visits will be assigned a day relative to this date.

Study day or relative day for a visit is defined as:

- Visit date date of Day 1 +1, if visit date ≥date of Day 1
- Visit date date of Day 1, if visit date <date of Day 1

There is no 'Day 0'

Study Day is calculated in reference to the date of randomization for efficacy analyses and date of first dose for safety analyses (efficacy analysis Study Day 1 = date of randomization; safety analysis Study Day 1 = date of first dose). Positive study days will count forward from Study Day 1. Study Day -1 will be the day before Study Day 1, and all subsequent negative study days will be measured backward from Study Day -1.

2.6. Baseline

Unless otherwise specified, baseline is defined as the last observation prior to the start of the first study drug administration. Change from baseline will be defined as (post-baseline value – baseline value).

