9.3.2. Safety Analyses

Participants who receive at least 1 dose of study drug will be analyzed for safety. The safety parameters to be evaluated are the incidence, intensity, and type of AEs, vital signs measurements, and clinical laboratory results. Exposure to study drug and reasons for discontinuation of study treatment will be tabulated.

Adverse Events

The verbatim terms used in the eCRF by investigators to identify AEs will be coded using the Medical Dictionary for Regulatory Activities, Version 21.0 or later. and will be graded according to the NCI-CTCAE, Version 4.03. Treatment-emergent AEs are AEs that occur or worsen on or after first dose of study drug through 30 days after the last dose of study drug. All reported intervention-emergent AEs will be included in the analysis. For each AE, the percentage of participants who experience at least 1 occurrence of the given event will be summarized by intervention group. In addition, comparisons between intervention groups will be provided if appropriate.

Treatment-emergent AEs will be summarized by system organ class, preferred term, toxicity grade, and relationship to study drug. Serious adverse events and deaths will also be summarized. Summaries, listings, datasets, or participant narratives may be provided, as appropriate, for those participants who die, who discontinue intervention due to an AE, or who experience a severe or a SAE.

Clinical Laboratory Tests

Laboratory data will be summarized by type of laboratory test. Descriptive statistics will be calculated for each laboratory analyte at baseline and for observed values and changes from baseline at each scheduled time point. A listing of participants with any laboratory results outside the reference ranges will be provided. A listing of participants with any markedly abnormal laboratory results will also be provided. Normal ranges will be used to identify values that are outside the normal ranges and abnormal laboratory results will be graded according to the NCI-CTCAE Version 4.03. A shift summary of baseline grade by maximum post-baseline CTCAE grade will be presented. For each laboratory parameter, the baseline laboratory value will be defined as the last laboratory value collected on or prior to the date of the first dose of study drug. Participants who develop toxicities of Grade ≥3 will be listed.

Electrocardiogram

Electrocardiogram data will be summarized by ECG parameter at screening (baseline) only.

Vital Signs

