6.1. Adverse Events

Subjects will be assessed for adverse events while on the study. Adverse events (AEs) will be graded according to the NCI Common Terminology Criteria for Adverse Events (CTCAE) version 4.03 and coded to preferred term and system organ class (SOC) using the MedDRA version 20.0 or later. All AEs reported on or after the date of first dose until 30 days (inclusive) after the last dose of study drug will be considered treatment-emergent and will be summarized by treatment group.

For each treatment group, AE incidence rates will be summarized with frequency and percentage by SOC and preferred term, with all subjects treated in that treatment group as the denominator, unless otherwise specified. In addition, AE incidence rates will also be summarized by severity and relationship to study drug. Treatment-related AEs are those judged by the Investigator to be at least possibly related to the blinded study drug. AEs with missing severity or relationship to study drug will be classified as severe and treatment-related, respectively. Subjects with multiple occurrences of events will only be counted once at the maximum severity to study drug for each preferred team, SOC. Deaths that occur within 30 days after the last dose of study drug are defined as on-study deaths.

Summary tables of the following AEs will be provided:

Overall summary of AEs: the number and percentage of subjects who experienced any AE including COVID-19, number of subjects with Grade 3/4 AEs, any serious adverse event

22

^b Placebo subjects treated with apalutamide + ADT after cross-over

^c Subjects treated with apalutamide + ADT including subjects from original apalutamide arm and subjects crossed over from placebo arm

(SAE) including COVID-19, any treatment-related AE, treatment related Grade 3/4 AE, any treatment-related SAE, AE leading to treatment discontinuation including COVID-19, related AE leading to treatment discontinuation, AE leading to death including COVID-19, related AE leading to death, and all deaths within 30 days of last dose

- All AEs by SOC and preferred term
- All AEs by SOC, preferred term, and toxicity grade
- Grades 3 or 4 AEs by SOC and preferred term
- Grades 3 or 4 AEs by decreasing frequency of preferred term
- Treatment-related AEs by SOC and preferred term
- Treatment-related AEs by SOC, preferred term, and toxicity grade
- Treatment-related AEs by decreasing frequency of preferred term

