6.2. Clinical Laboratory Tests

The number and percentage of subjects with abnormal laboratory values will be summarized. The number and percentage of subjects with parameters with predefined NCI-CTCAE (version 4.03)

toxicity grades of \geq 3 may also be summarized. For selected key laboratory measurements, changes in toxicity grade from baseline to the worst grade experienced by the subject during the Treatment Phase and the Study will be summarized using shift tables.

A listing of subjects who develop toxicities of Grade ≥ 3 will be provided for each laboratory parameter.

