6.3. Vital Signs and Physical Examination Findings

Each vital sign (temperature, blood pressure (systolic and diastolic), respiration rate, and heart rate) at baseline will be summarized and presented by treatment group. The number and percentage of subjects with values beyond clinically important limits (defined in Table 2) will be summarized.

Table 2 Clinically Significant Abnormality For Vital Signs

Parameter	Criteria	
Systolic blood pressure	 Absolute result > 160 mmHg and increase from baseline of > 20 mmHg Absolute result < 90 mmHg and decrease from baseline of > 20 mmHg 	
Diastolic blood pressure	 Absolute result > 100 mmHg and increase from baseline of > 10 mmHg Absolute result < 50 mmHg and decrease from baseline of > 10 mmHg 	
Weight	 5 - < 10% weight loss from baseline 10 - < 20% weight loss from baseline >= 20% weight loss from baseline 	

Abnormal findings in physical examination will be recorded and summarized as AEs.

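### The safety baseline is not reset at cross-over, so baseline-referenced summaries in the two columns holding crossed-over men include change that arose on placebo

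*SAP*

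**What the plan says.** **Baseline.** SAP section 2 says "Unless otherwise specified, baseline value is defined as the closest measurement prior to the first dose of study drug" and adds "The first dose starts on Day 1 of Cycle 1". SAP 2.6 repeats the rule: "Unless otherwise specified, baseline is defined as the last observation prior to the start of the first study drug administration". Protocol 9.3.2 uses the same anchor for laboratory data: "baseline laboratory value will be defined as the last laboratory value collected on or prior to the date of the first dose".

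**Outputs that use it.** The shift tables in SAP 6.2 summarise "changes in toxicity grade from baseline to the worst grade experienced by the subject during the Treatment Phase"; they name the Study as a further window. SAP 2.1 runs the Treatment Phase from Cycle 1 Day 1 until study drug is stopped. The criteria in SAP 6.3 Table 2 are relative to baseline, for example "Absolute result > 160 mmHg and increase from baseline of > 20 mmHg"; the weight-loss bands are too. Protocol 9.3.2 adds changes from baseline at each scheduled time point for laboratory values and blood pressure.

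**Columns.** SAP section 6 presents safety in four groups. By its footnotes, *Placebo* covers the time before cross-over. *Placebo to Apalutamide* is "Placebo subjects treated with apalutamide + ADT after cross-over". *Apalutamide Treated* pools the original apalutamide arm with the crossed-over men.

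**Clock.** SAP 2 and 2.5 set safety Study Day 1 at the first dose, and SAP 2.1 says "Nominal visits will be used to display the safety data".

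**The concern.** The SAP sees that cross-over changes what a man is exposed to and creates two columns for it. It does not carry this through to the variables shown in them. For a control participant the first study drug dose is placebo. After the switch, his laboratory grades, blood pressure and weight are still compared with values taken before placebo began. A change that developed on placebo plus ADT and persisted is then shown under apalutamide.

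Both SAP baseline definitions allow for another rule where one is specified, but neither SAP 6.2 nor 6.3 specifies one.

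Safety, including laboratory abnormalities, is a secondary objective, and the study is a post-approval commitment to provide data in Chinese participants. The crossed-over men are about a third of those exposed to apalutamide in this study.

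**Working it through.** **1. How many men are affected.** Protocol 4.2.1 puts about 25 of 75 participants on placebo and takes 6.2% as having metastasis at the first scan without prior PSA progression. 0.062 × 25 = 1.55, which reproduces the protocol's figure of 1-2. That leaves 25 × 0.938 = 23.45 men crossing over. With about 50 men in the original apalutamide arm, their share of the pooled column is 23.45 / 73.45 = 32% (at most 25 / 75 = 33%). One man is 1 / 23.45, or about 4 points, of *Placebo to Apalutamide*.

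**2. How far the baseline precedes apalutamide.** The maximum is 5 cycles × 28 days = 140 days. For the mean, take the exponential TTPP with a 3.7-month median (112.6 days) from protocol 9.1.
- *Continuous detection, switch at progression or 140 days.* With rate ln 2 / 3.7 = 0.187 per month and T = 140 / 30.4375 = 4.60 months, the mean is (1 − e^(−0.187 × 4.60)) / 0.187 = 3.1 months, about 94 days.
- *PSA drawn as in Schedule of Activities footnote 8.* Samples at Cycle 2, 3 and 4 Day 21 are days 49, 77 and 105. Cumulative progression is 1 − 2^(−t/112.6) = 26%, 38% and 48%. Switches at Cycle 3, 4, 5 or 6 Day 1 follow 56, 84, 112 or 140 days of placebo. Mean = 0.260 × 56 + 0.117 × 84 + 0.099 × 112 + 0.524 × 140 = 109 days (3.6 months).
- *The same, with confirmation one visit later.* 0.260 × 84 + 0.117 × 112 + 0.623 × 140 = 122 days (4.0 months).

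So the mean is roughly 3 to 4 months.

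**3. What the rule does to one man.** This is a constructed example to show the mechanism, not a typical patient. Weight is 80.0 kg at Cycle 1 Day 1, 76.5 kg at a Cycle 6 Day 1 switch and 75.8 kg at Cycle 9 Day 1. From the stated baseline the loss is 4.2 / 80.0 = 5.3%, which falls in the 5 to <10% band. Since starting apalutamide it is 0.7 / 76.5 = 0.9%. The other 3.5 / 80.0 = 4.4% arose on placebo.

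**4. Possible size.** The documents give no placebo rate for the SAP 6.3 thresholds or for laboratory grade shifts. Assume that a share q of the 23.45 men first reaches a threshold on placebo, that the change persists, and that none of them would have reached it on apalutamide anyway. Men carried over = 23.45 × q; maximum inflation of the pooled column = 23.45 × q / 73.45.
- q = 5%: 1.2 men, 1.6 points
- q = 10%: 2.3 men, 3.2 points
- q = 20%: 4.7 men, 6.4 points
- q = 30%: 7.0 men, 9.6 points

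**5. Worst-grade window.** Read alone, SAP 6.2 covers the whole Treatment Phase and Study, which for a crossed-over man includes placebo. Footnotes a and b to the column table split the data at cross-over. The two cannot both define the window, and no text says which governs.

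**The case against.** The best defence is that footnotes a and b already split the columns by period, so a sensible programmer would use only post-switch values in *Placebo to Apalutamide*. This stands as far as it goes. It means a reader should not infer that worst grade certainly spans both treatments in that column; the documents contain a conflict, not a settled rule. But the footnotes govern which values enter the column, not the value they are compared with. The baseline problem survives them.

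Three stronger readings are tempting, and the documents do not support them.
- *That adverse event rates under apalutamide are inflated.* One could scale the global study's placebo rates (21% hypertension, 6.5% weight decreased) to the placebo period. Those are adverse event incidences. Adverse event tables do not use this baseline, and events starting on placebo fall before cross-over. The affected outputs are measured thresholds and laboratory shifts, for which no placebo rate is given.
- *That the visit clock moves placebo changes into apalutamide columns.* It does not. Nominal visits only misalign time on drug: at Cycle 7 Day 1 an original apalutamide man has had 24 weeks of drug, and a man switched at Cycle 6 Day 1 has had 4. SAP 6.2 and 6.3 plan no by-visit means. Protocol 9.3.2 does, but the SAP applies the four columns only where appropriate.
- *That apalutamide safety reporting as a whole is compromised.* The randomised *Apalutamide* column is untouched. Counts of abnormal laboratory values, and Grade 3 or higher counts and listings, do not refer to baseline. The SAP plans no inference on safety data unless otherwise specified.

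**Conclusion.** The concern holds for a defined set of outputs: laboratory shift tables, blood pressure and weight threshold counts, and change-from-baseline summaries, wherever they are shown for *Placebo to Apalutamide* or *Apalutamide Treated*. Followed literally, both documents compare about 23 men with values taken up to 140 days before their first apalutamide dose. Separately, the worst-grade window in SAP 6.2 must be reconciled with the column footnotes.

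The missing reset is certain from the text. Its numerical effect is unknown; the 1 to 7 men above depend on an assumed 5 to 30%. The mean lead-in depends on the exponential assumption and on how quickly progression is detected and confirmed. The primary TTPP analysis is not affected. This should be corrected because the SAP's own columns need it and the data already exist.

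**What to change.** Amend SAP 2.6, 6.2 and 6.3, and align protocol 9.3.2:
- For *Placebo to Apalutamide*, and for crossed-over men in *Apalutamide Treated*, define baseline as the last value on or before the first apalutamide dose. Take worst grade and threshold crossings only from values after that dose.
- For *Placebo*, keep the pre-placebo baseline and use only values up to the first apalutamide dose.
- Count relative day and treatment duration for the apalutamide period from the first apalutamide dose (SAP 2, 2.5, 4.3 and 4.4). Where by-visit summaries are shown for these columns, use time since that dose.

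The cost is wording in both documents and some added programming: a period-specific baseline flag, data window and relative day. No new data, visits or participants are needed. Hematology, chemistry, blood pressure and weight are scheduled at Day 1 of Cycles 1 to 6, so a recent value should exist at any switch visit.

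There is one limitation. TSH, lipids and testosterone are drawn only every 4 cycles, so men switched before Cycle 5 Day 1 keep their Cycle 1 Day 1 value for those tests. Under the stated median that is 26.0% + 11.7%, about 38% of men, or 26% if confirmation takes one more visit. The tables should say so.
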